### 6.1.2 Subject recruitment into study

Once the site has determined that the patient meets the inclusion/exclusion criteria, the patient will be scheduled for their  $90 \pm 14\,$  day follow-up visit and echocardiogram, at which point they may be approached by the study staff for verification of inclusion/exclusion and for consent into the study.

- 6.1.3 Steps for screening and consent of patients:
  - 1) A chart review of patients prescribed the WCD (in the last 30 days) after hospitalization for HF will be used to evaluate patients for enrollment into the pre-study registry.
  - 2) Potentially eligible patients from the registry will be scheduled for a 90  $\pm$  14 day follow-up visit and echocardiogram.
  - 3) If eligible, at the 90  $\pm$  14 day follow-up visit, patients will be consented and enrolled into the study.

#### 6.2 Scheduled Visits

- 6.2.1 Clinical and EF reassessment at pre-specified timepoints
  - 6.2.1.1 Upon enrollment into the pre-study registry, baseline clinical data will be recorded from chart review and patient interview if necessary.

6.2.1.2 After enrollment into the study, additional clinical data will be recorded from chart review and patient interview if necessary at 90, 120, 150, 180, 270 and 360 days post WCD start. This data will include medications, ER visits, HF hospitalizations, survival, ICD placement, and last known clinical status.

A subset of sites will also collect quality of life (QOL), patient reported data at baseline (registry enrollment), 90 (±14), and 180 (±14) days of WCD use. QOL data from 350 enrolled patients (from US and Europe) will be collected using the Kansas City Cardiomyopathy Questionnaire (KCCQ-12).

- 6.2.1.3 EF measurement at 90 ( $\pm$ 14), 180 ( $\pm$ 14) and 360 ( $\pm$ 14)-days post WCD start will be requested and recorded. Any additional EF measurements taken at the end of WCD use will be collected as well, if not at one of these already pre-specified timepoints (see 6.3.1.2).
  - 6.2.1.3.1 Echocardiographic assessment of LVEF is most common. Nevertheless, other imaging modalities (MUGA, MRI) may be used to document LVEF at day 0. Although there are likely to be differences in EF assessment among enrolling sites and practices, these differences are not expected to affect the outcome of the trial. At a minimum, we will request a 2-D echo at the scheduled time-points.

The following scheduled visit is for all registry patients:

6.2.2 Visit post-index hospitalization (day 0 - 30 from WCD start)

- 6.2.2.1 Inclusion/exclusion will be verified.
- 6.2.2.2 Informed Consent for registry will be obtained.
- 6.2.2.3 Clinical history data will be collected, including current Echo and ECG data.
- 6.2.2.4 Medication usage will be collected
- 6.2.2.5 QOL data will be collected (subset of patients only)

The following scheduled visits are for all study patients, regardless of ongoing WCD use, and include:

- 6.2.3 Visit 1 Enrollment (day 90 ± 14 from WCD start)
  - 6.2.3.1 Inclusion/exclusion will be verified.
  - 6.2.3.2 Informed Consent will be obtained.
  - 6.2.3.3 Clinical data will be collected, including current Echo and ECG data.
  - 6.2.3.4 Medication usage will be collected and any adjustments made to achieve GDMT.
  - 6.2.3.5 QOL data will be collected (subset of sites only)

For patients who will be continuing WCD use only:

6.2.3.5 Medical orders and dispensing of the WCD will follow current commercial procedures.

 Spertus and Jones. Development and Validation of a Short Version of the Kansas City Cardiomyopathy Questionnaire. Circ Cardiovasc Qual Outcomes. 2015;8:00-00.

6.2.4	Patient intervi	lews through follow-up phone calls or office visits (days 120 $\pm$ 14 and 150 $\pm$ start)
	6.2.4.1	Clinical data will be collected
	6.2.4.2	Medication changes will be collected
	6.2.4.3	Device information, adverse events, and cardiac event information will be collected as needed
6.2.5	Visit 2 (day 18	30 ± 14 from WCD start)
	6.2.5.1 6.2.5.2	Clinical data will be collected, including current Echo.  Medication changes will be collected.
	6.2.5.3	Device information, adverse events, and cardiac event information will be collected.
	6.2.5.4	If patient has recently ended the study, or WCD use, reasons will be collected.
	6.2.5.5	QOL data will be collected (subset of patients only)
6.2.6	Patient intervi	iew through follow-up phone calls or office visits (day 270 $\pm$ 14 from WCD
	6.2.6.1	Clinical data will be collected.
	6.2.6.2	Medication changes will be collected.
	6.2.6.3	Device information, adverse events, and cardiac event information will be collected.
	6.2.6.4	If patient has recently ended the study, or WCD use, reasons will be collected.
6.2.7	Visit 3 (day 36	60 ± 14 from WCD start)
	6.2.7.1	Clinical data will be collected, including current Echo.
	6.2.7.2	Medication changes will be collected.
	6.2.7.3	Device information, adverse events, and cardiac event information will be collected.
	6.2.7.4	If patient has recently ended the study, or WCD use, reasons will be

#### 6.3 Unscheduled Visits

Unscheduled visits for registry or study patients may include:

collected.

6.3.1 Resuscitation from SCA event, death, inappropriate shock, and unanticipated end of WCD use or study completion (immediately following notification of occurrence)

6.3.1.1	In the event of a WCD recording that indicates shock, sustained VT/VF >30
	seconds with no shock, or asystole (<10 BPM), sites will be notified from
	ZOLL of the occurrence, and ECG strips will be sent.

- 6.3.1.2 Clinical data will be collected, including any additional EF measurements that were taken at the end of WCD use.
- 6.3.1.3 Device information, adverse events, and cardiac event information will be collected.
- 6.3.1.4 At the end of the study or WCD device use, the reason for discontinuing will be recorded.

## 6.4 Long-term Clinical Outcome Assessment

Final survival assessment will be 1 year from WCD start of use, ± 14 additional days.

6.4.1 Sites will be asked to determine survival for all patients enrolled in the study through either routine medical records and appointments, or a phone call to the patient.

## 6.5 Study Procedures Flowchart (or Table)

Table 1. Study Procedures Table for WCD Pre-study Registry

Table 1. Study Procedures Table for WCD Pre-study Registry						
	Timing of Data Collection (post WCD start)					
Data Collected	Initial	WCD end				
	Visit (0-30d)					
Screening	X					
(Inclusion criteria,						
exclusion criteria,						
consent)						
Baseline data	X					
(Demographics,						
Echo, ECG, and						
clinical						
characteristics)	37					
Echo data	X					
Medications	X	X				
QOL data	X (subset of sites only)					
End of WCD use		X				
data (Medical or						
patient reason for						
ending use,						
compliance)						
Defibrillation data-		X				
WCD						
(Appropriateness,						
consciousness,						
effectiveness,						
clinical status)						

Table 2. Study Procedures Table for HF Opt study

Data Collected	Enrollment Visit (90d)	120d call	150d call	180d visit	270d visit	360d visit	WCD end
Screening (Inclusion criteria, exclusion criteria, consent)	X	Call	Call	VISIL	VISIT	visit	Circ
ECG	X						
Follow-up Echo data	X			X		X	X*

Clinical Status	X	X	X	X	X	X	X
(Medical care							
utilization,							
Medications,							
Symptoms, ICD							
implantation, SCA							
QOL data (subset	X			X			
of sites only)							
End of WCD use							X
data (Medical or							
patient reason for							
ending use,							
compliance)							
Defibrillation data-	X	X	X	X	X	X	X
ICD or WCD							
(Appropriateness,							
consciousness,							
effectiveness,							
clinical status)							
HF diagnostics							X
(Activity, position,							
heart rate metrics)							
Long-term survival						X	X
status							
* If echo performed at end of WCD use, and not at one of the pre-specified timepoints							

6.6 Blinding and Unblinding of Study

NA

## 7 Study Device Management

The prescription of the study device will be written by the same treating physician who prescribed the device for the first 90 days. Alternatively, another physician at the study site, such as one of the study site investigators, may prescribe the device if the original prescribing physician is no longer available.

## 7.1 Subject Compliance Monitoring

Patient compliance with the WCD will be assessed through the device records. The WCD compiles compliance data by recording the amount of time the WCD is worn each day. This data, along with the recorded ECG data, is then downloaded to the ZOLL database.

Patient adherence with taking HF medications will be assessed through patient interview at regular intervals. All subjects will be followed regardless of compliance.

Patients who receive an ICD early (prior to reaching GDMT or not otherwise having an indication for an ICD) versus continuing WCD as described by the protocol will not be considered withdrawn from the study, and will continue to be followed.

Patients who refuse an ICD or WCD continuation as described by the protocol (EF  $\leq$  35%) will not be considered withdrawn from the study, and will continue to be followed.

## 7.2 Managing WCD Therapy

Since this is an observational, unblinded study, WCD therapy will be handled following normal commercial procedures. However, sites will be notified if a patient receives a shock, and ECG recordings of the event will be sent for the completion of the SCA/Defibrillation event CRF. Evaluation and treatment of patients receiving a shock will be determined by the treating physician.

Treatment events will be initially determined to be appropriate or inappropriate by each site's principal investigator. All shocked events and terminal ECG recordings will be adjudicated by a committee independent of the sponsor. Information regarding the treatment event will be captured in the SCA/Defibrillation event CRF.

## 7.3 Dispensing, Storage and Return

#### 7.4.1 Dispensing of Study Device

Medical orders and dispensing of the WCD will follow current commercial procedures.

### 7.4.2 Storage

NA

#### 7.4.3 Return of Study Device

At the completion of the WCD portion of the study, return of the WCD will follow current commercial procedures.

#### 7.4 Device Malfunction or Defect

The WCD System continuously monitors and records critical patient data to help diagnose and treat arrhythmic conditions. Device data will be uploaded at least weekly to a central server located in Pittsburgh, PA. In the event that uploads are not occurring on a routine basis, subjects should call ZOLL Technical Support [contact]) (for Germany call, [name]) for instructions.

[figure not shown]
Subjects having questions or difficulty managing their WCD should be referred to the patient manual or instructed to call ZOLL Technical Support [contact]) (for Germany call, [name]).

#### 8 Statistical Plan

#### 8.1 Sample Size and Power Calculation

The total number of WCD prescriptions for the study is estimated to be 868, and assuming ~15% lost follow up, 738 patients will have an EF measurement at day 90. The sample size was calculated using data-based estimates as described below.

#### 8.1.1 Statistical design used for sample size calculation

This dataset will be used evaluate among all patients, if more than 5% of them will experience EF improvement between 90 and 180 days ( $n_5/n > 5\%$ ).

To calculate the number of samples (n), we first calculated  $n_4$ , then calculated n based on the following formula:

$$n = \frac{n_4}{P_{followup2}} * \frac{1}{p_{wcd}} * \frac{1}{P_{followup1}}$$

where  $p_{wcd}$  is the percentage of patients who will wear WCD beyond 90 days ( $n_1/(n_1+n_2+n_3)$ ,  $p_{followup1}$  and  $p_{followup2}$  are the percentage of patients with proper follow up from 0 to 90 days and from 90 days to 180 days respectively, both of the them equals to 0.85 (1-0.15=0.85).

To calculate sample size for  $n_4$ , we performed superiority test. The statistical hypothesis to be tested is:

[figure not shown]
$$H0: P \le P_0 + \delta \text{ vs } H1: P > P_0 + \delta$$

The sample size of superiority test is calculated as the following formula:

$$n_4 = p(1-p) \left( \frac{Z_{1-\alpha} + Z_{1-\beta}}{p - p_0 - \delta} \right)^2$$

where p is the actual proportion of patients who will have EF improvement ( $n_5/n_4$ ).  $p_0$  is the baseline proportion, and specified as 0.001 (close to 0).  $\delta$  is the test margin, since the hypothesis is that more than 5% of them will experience EF improvement between 90 and 180 days ( $n_5/n > 5\%$ ),  $\delta$  depends on  $p_{wcd}$  as  $\delta = 0.05/P_{wcd}$ . We also specify  $\alpha$  as 0.05,  $\beta$  as 0.1

As shown in figure above, sample size (n) depends both on p, the actual proportion of patients who will have EF improvement (p=n5/n4) and  $p_{wcd}$ , the percentage of patients who will wear WCD beyond 90 days ( $p_{wcd} = n_1/(n_1+n_2+n_3)$ ).In this study, we specify  $\alpha$  as 0.05,  $\beta$  as 0.1. We predict that about 1/3 patients will have continued WCD wear from 90 to 180 days; and actual proportion of WCD patients at 90 days to have further EF improvement is 23%. In this case, we plan to prescribe WCD to 868 patients (initial registry sample size), in order to have approximately 738 patients eligible for the study at day 90. If mid-study analysis shows continued WCD use to be far out of 1/3, then sample size will be re-adjusted as necessary.

Initial registry sample size vs p, the actual proportion of patients who will have EF improvement between 90 and 180 days and  $p_{wcd}$ , the percentage of patients who will wear WCD beyond 90 days.

When the number of patients in WCD group is around ~250, with an estimated rate of shock at 1.5%, the probability of observing two or more events is more than 90%. When the number of patients in WCD group is around 200, with an estimated rate of shock at 1.5%, the probability of observing two or more events is ~80%.

Sample size adjustment (mid-term analysis): As both the dropout ratio prior to the registry and the percentage of patients who will wear the WCD beyond 90 days were higher than predicted, the sample size for the registry and study were recalculated in this protocol revision (version C). The final goal remains to have 200-250 patients in the extended wear WCD group as determined in the preceding paragraph.

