## 5.2 Study Size

Up to 1400 subjects will be enrolled into the pre-study registry, and up to 600 may be enrolled in the study portion. Thirty to eighty sites will enroll patients into the study. Sites will initially be located in the United States and Germany, but may be expanded to other European countries. Individual sites will only be allowed to enroll up to 140 patients (or 10% of the total population).

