#### 8.6.3 Handling missing data

- 8.6.3.1 Loss to follow-up has been anticipated in the sample size calculation.
- 8.6.3.2 Missing data will not be replaced by any algorithm.

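### The registry size of 868 (738 at day 90) does not follow from the printed formula, which gives about 1,009 (858), and the version C recalculation restates no power for the EF hypothesis

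*Combined protocol and SAP*

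**What the plan says.** Section 8.1 states "The total number of WCD prescriptions for the study is estimated to be 868" and that about 15% loss leaves 738 patients with an EF measurement at day 90. Section 8.1.1 derives this in two steps. A one-sided superiority formula gives n4, the number of extended wearers needed to show that more than 5% of all patients improve between days 90 and 180. That number is then divided by the wear fraction and by two follow-up fractions to give n. The section concludes "we plan to prescribe WCD to 868 patients (initial registry sample size), in order to have approximately 738 patients eligible".

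The next paragraph turns to shocks. With about 250 wearers and a 1.5% shock rate it says "the probability of observing two or more events is more than 90" per cent; with 200 it says about 80%.

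The mid-term adjustment paragraph then reports that dropout before the registry and "the percentage of patients who will wear the WCD beyond 90 days were higher than predicted", and that both sizes were recalculated for version C. It adds: "The final goal remains to have 200-250 patients in the extended wear WCD group as determined in the preceding paragraph". Section 5.2 gives the current sizes: "Up to 1400 subjects will be enrolled into the pre-study registry, and up to 600 may be enrolled in the study portion". Section 8.6.3 relies on this calculation: "Loss to follow-up has been anticipated in the sample size calculation".

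**The concern.** Section 8.1 is the only justification of study size, and it raises three problems.

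- The stated 868/738 is not what the printed formula returns from the printed inputs.
- The version C recalculation appears only as an outcome. No new improvement proportion, wear fraction, loss or power is given. The paragraph to which the text attributes the 200-250 goal concerns shocks, not EF. The text also does not say whether 200-250 counts wearers before or after the 90-180 day loss.
- One of the two shock probabilities supporting that goal is overstated.

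As written, a reader cannot reproduce the size. The reader may also take 868/738 as current beside 1400/600, although 738 eligible at day 90 exceeds the cap of 600. And the reader may assume that 90% power for the EF hypothesis still holds in version C, which the documents do not show.

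**Working it through.** **Inputs, all from Section 8.1.1.** p = 0.23; p0 = 0.001; P_wcd = 1/3 (given as approximate); δ = 0.05/P_wcd = 0.15; α = 0.05, one-sided (Z = 1.645); β = 0.1 (Z = 1.282); both follow-up fractions 0.85.

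**1. The plan's figure by its own formula.**

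- n4 = p(1−p)·[(1.645 + 1.282)/(p − p0 − δ)]² = 0.23 × 0.77 × (2.927/0.079)² = 243.0
- n = n4/0.85 × 3/0.85 = 1,009
- Day 90: 1,009 × 0.85 = 858

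The stated pair is internally consistent (868 × 0.85 = 737.8), but 868 is 14% below 1,009. Working back from 868: 737.8/3 = 245.9 wearers at day 90, and × 0.85 = 209 evaluable, against the 243 required. At 209 the printed formula gives 86% power; an exact one-sided binomial test gives 89.5%.

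**2. What could explain 868.**

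| Change | n |
|---|---|
| Two-decimal rounding of P_wcd (0.33 to 0.34) | 1,060 to 920 |
| Rounding of p (0.225 to 0.235) | 1,132 to 906 |
| P_wcd = 0.344, both losses kept | about 868 |
| p = 0.237, both losses kept | about 868 |
| 90-180 day loss left out | 858 |
| Arcsine method (n4 = 209.5) | 870 |
| Exact binomial, first n4 reaching 90% (210) | 872 |
| Exact binomial, n4 from which power stays at 90% or more (229) | 951 |
| Null-variance normal test | 847 |

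Several routes come close, and the text names none of them.

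**3. EF power at the version C goal.** Power = Φ[(p − p0 − 0.05/P_wcd)·√n4/√(p(1−p)) − 1.645]. With p = 0.23 and P_wcd = 1/3:

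| Goal | Evaluable | Formula | Exact |
|---|---|---|---|
| 200, counted before 15% loss | 170 | 79% | 80% |
| 250, counted before 15% loss | 212 | 86% | 88% |
| 200, counted after loss | 200 | 84% | 86% |
| 250, counted after loss | 250 | 91% | 94% |

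These figures are illustrative, because the plan says wear exceeded the prediction. A larger P_wcd lowers δ. If p stays at 0.23, formula power reaches 90% at P_wcd = 0.372 with 170 evaluable and at 0.346 with 212. At P_wcd = 250/600 = 0.417 with 212 evaluable it is 98%.

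The answer turns on p. Suppose instead that the all-patient gain stays at 0.23/3 = 7.67%, which is an assumption not made in the documents. Then p at P_wcd = 0.417 is 0.0767/0.417 = 0.184, and power with 212 evaluable is 77% by formula and 79% exact.

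**4. Shock probability.** P(X ≥ 2) = 1 − 0.985^N − N × 0.015 × 0.985^(N−1).

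- N = 200: 80.3%, which agrees with the plan.
- N = 250: 89.0%, against more than 90% stated.
- N = 258 is the first size to reach 90%.

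**The case against.** The strongest reply is that 868 may be right and only the displayed formula wrong. The effect size in the denominator is just 0.079, so n is very sensitive to small input changes. The wear fraction is given only as approximate, and 0.344 could pass for about a third. The arcsine and first-crossing exact methods give 870 and 872. The plan's chart of n against p and P_wcd is not in the text available for review and might show the inputs used. This stands: the discrepancy is not evidence that 868 is too small, and replacing it with 1,009 is not the only remedy. What remains is that the section presents the formula as the source of the number, and it is not.

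It can also be said that the 200-250 goal matches the EF calculation, since 246 wearers at day 90 and 209 after loss both fall in that range. That is so, but the text attributes the goal to the shock paragraph and does not make this link.

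Higher wear would raise EF power if p held at 23%, so no shortfall is shown. That is correct, but the plan does not report p, and the 77% to 98% range above shows how much depends on it.

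Finally, Section 8.3.1 analyses EF descriptively and no test of the 5% threshold is specified, so nominal power governs no decision rule. This lowers the stakes. It does not remove the claim, because Sections 3.1 and 3.2.2 state the hypothesis and Section 8.1.1 assigns it α and β. The shock error is about one percentage point at an approximate N and is minor by itself.

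**Conclusion.** The concern holds. Two stated figures are wrong as written: 868/738 does not follow from the printed formula and inputs, which give 1,009/858, and the chance of two or more shocks at 250 wearers is 89.0%. The practical shortfall behind 868 is small if P_wcd is 1/3 and p is 0.23: 86% power by formula or 89.5% exact, against 90% intended.

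The version C point is a reporting gap, not demonstrated under-powering. Under the documents' original p and P_wcd, formula power at 200-250 wearers runs from 79% to 91%, depending on the number and on whether it is counted before or after loss. It is higher if wear rose and p held, and could be near 77% if wear rose and the all-patient gain did not. The documents do not say which applies.

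**What to change.** In Section 8.1:

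- Label 868/738 as the superseded calculation. Either correct it to about 1,009/858, or state the unrounded inputs and the method for n4 that produce 868.
- For version C, state p, the wear fraction seen at the mid-term analysis and both losses. Say whether 200-250 counts wearers before or after the 90-180 day loss. Then give the EF power at 200 and at 250 wearers under the cap of 600, in place of the implied 90%.
- Change the shock probability at 250 to about 89%.

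The cost is wording plus one recalculation from mid-term figures the sponsor should already hold. No extra patients are needed. The restated figures may be slightly less favourable than those now printed.

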#### 8.2 Randomization Scheme

Because WCD's have been shown to be very effective at treating potentially lethal ventricular tachyarrhythmias and are already FDA-approved for use in the study population, randomization will not be done.

## 8.3 Endpoint Assessment

## 8.3.1 Primary Endpoint – LVEF recovery and GDMT

Descriptive or summary statistics of serial EF measurements will be used to analyze the rate of recovery of ventricular dysfunction following discharge. For example, the means of EF at 180 days will be compared to the means of EF at baseline and 90 days. The percentage of patients reaching the goal of EF>35% will be compared at 90 days and 180 days. Also, the time taken to reach EF>35% will be calculated for those who improve, and compared between groups (based on baseline characteristics). Individual patient EF measurements over time will be compared to determine whether common patterns arise in certain groups of patients (fast recovery/slow recovery, plateaued recovery/peaked recovery followed by decline). The influence of baseline characteristics on the potential for recovery will be evaluated.

Descriptive statistics will be used to assess the degree GDMT was reached at 90 and 180 days, and how GDMT relates to EF recovery. We will also assess how adherence to the GDMT regimen affects EF recovery and overall clinical improvement.

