## 2 Study Objectives

## 2.1 Primary Objective(s)

The primary objective of this study is to observe the rate of recovery of ventricular function (EF>35%) between 90 and 180 days in newly diagnosed HF with reduced EF patients who were prescribed the WCD while being initiated on their HF medications. This will be measured from EF closest to before hospital discharge, then at 90, 180 and 360-days after WCD start, regardless of continued WCD use, prior EF improvement, or ICD implantation. While approximately one-third of the patients will likely experience EF recovery in the first 90 days, we hypothesize that an additional 5-10% of patients will experience EF improvement between 90 and 180 days as GDMT is achieved. This would be considered clinically significant in terms of the potentially avoided ICD implantations. Outcomes will be tracked and reported for three pre-specified groups based on assessment of SCD risk at 90 days of WCD use:

- 1) Patient improved (EF >35%), SCD risk deemed to be negligible. These patients are expected to end WCD use and not receive an ICD.
- 2) Patient improved EF from start of WCD use (a positive change of at least 5 percentage points in EF), or has a borderline EF of 30-35%, but still has continued SCD risk (EF ≤ 35%). These patients are expected to continue to use the WCD for an additional 3 months.
- 3) Patient not improved from start of WCD use (no change or worsening of EF), EF<30% and has continued high SCD risk. Those on GDMT are expected to be evaluated for an ICD. Those not yet on GDMT may continue the WCD for an additional 90 days.

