#### 3.2.2 LVEF recovery

To support our primary hypothesis that an additional 5% of patients will experience EF improvement between 90-180 days, EF measurement for all patients at 90 (±14), 180 (±14) and 360 (±14)-days after WCD start will be requested and recorded. For this study, EF>35% will be considered as EF improved.

- 3.2.2.1 Echocardiographic assessment of LVEF is most common. Nevertheless, other imaging modalities (MUGA, MRI) may be used to document LVEF at day 0. Although there are likely to be differences in EF assessment among enrolling sites and practices, these differences are not expected to affect the outcome of the trial. At a minimum, we will request a 2-D, M-mode echo at the scheduled time-points.
- 3.2.2.2 Echocardiogram core lab verification. EF is commonly estimated by echocardiogram. Several studies have shown EF measurement to have a wide range of variability that can be observer dependent. Study echocardiograms will be sent to a core lab for a uniform determination of the EF. The core lab determinations will be used to verify local estimates of EF and may be used in secondary analyses of the study data

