## 4 Study Subject

#### 4.1 Inclusion Criteria

The population for this study will be patients who had an ejection fraction (EF)  $\leq$  35% following hospitalization for newly diagnosed HF, and who have already been using a WCD for 90 days. Prior to 90 days, eligible patients will be enrolled into a registry. Registry patients will be enrolled during the first 30 days of WCD use.

All of the following must be true for enrollment into the registry (day 0 – 90 of WCD use):

- 4.1.1 Patients (≥18 years old) who were prescribed the WCD ≤ 10 days post-discharge after hospitalization for a primary reason of newly diagnosed HF with reduced EF (≤30 days since first HF hospitalization), with ischemic or nonischemic cardiomyopathy, and have used the WCD for no more than 30 days.
- 4.1.2 Patients who had an EF  $\leq$  35% during index hospitalization.

All of the following must be true for enrollment into the study (day  $90 \pm 14$ ):

- 4.1.3 Patients (≥18 years old) who were prescribed the WCD ≤ 10 days post-discharge after hospitalization for a primary reason of newly diagnosed HF with reduced EF (≤30 days since first HF hospitalization), with ischemic or nonischemic cardiomyopathy, and either 1) have already used a WCD for 90 ± 14 days or 2) were enrolled in the registry after 01-March-2019 and received an ICD prior to 90 days of WCD use.
- 4.1.4 Patients who had an EF  $\leq$  35% during index hospitalization. Of note, EF at 90  $\pm$  14 days post-hospitalization does not need to be low to be included in the study.

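### Section 8.3.1 compares time to EF>35% between baseline groups among improvers only, so a group can look slower while recovering as many or more patients at every visit

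*Combined protocol and SAP*

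**What the plan says.** Section 8.3.1 opens by calling the analysis of serial EF descriptive. Among several summaries it states that "the time taken to reach EF>35% will be calculated for those who improve, and compared between groups (based on baseline characteristics"). It gives no summary measure, no test, and no rule for patients who do not reach EF>35%, who die first or who lack an EF.

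Two other sentences in the same paragraph are relevant:

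- "The percentage of patients reaching the goal of EF>35% will be compared at 90 days and 180 days". This is not stated to be by baseline group and does not include day 360.
- "The influence of baseline characteristics on the potential for recovery will be evaluated". This is not limited to improvers, but no method, denominator or time point is given.

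The data would support more. Section 3.2.2 says "EF measurement for all patients at 90 (±14), 180 (±14) and 360 (±14)-days after WCD start will be requested and recorded". Kaplan-Meier and survival methods are named in section 8.3.6 for mortality only, and section 8.4 adds no further method.

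**The concern.** Selecting patients who improve and then comparing their times conditions on the outcome. A patient who never recovers costs the group nothing, while a patient who recovers at day 180 instead of never makes the group's average time longer. More recovery can therefore register as slower recovery.

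Section 1.3 lists as open questions when to implant an ICD and how often and when to measure EF recovery. The study hypothesis concerns extra recovery between days 90 and 180. A baseline group with more of that late recovery is the group of interest, and this comparison can present it as the slow one.

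**Working it through.** The documents give no expected result for this comparison, so there is no figure to reproduce. The check is an illustration built on the protocol's own rates.

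**Inputs from the documents**

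- Day-90 recovery (section 2.1): "approximately one-third of the patients will likely experience EF recovery in the first 90 days".
- Later recovery (section 2.1): "we hypothesize that an additional 5-10% of patients will experience EF improvement between 90 and 180 days as GDMT is achieved".
- EF visits at days 90, 180 and 360, each ±14 days (section 3.2.2).
- Up to 600 study patients (section 5.2), and a follow-up proportion of 0.85 from day 90 to day 180 (section 8.1.1).

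**Assumptions**

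- Section 2.1 gives 5-10% as a range for one overall rate. Giving different values from it to two baseline groups is my assumption.
- The scheduled day is used as the time, and no one first recovers after day 180.
- There are two groups of equal size.

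**Formula.** Let r be the proportion recovered by day 90 and l the proportion first recovered by day 180. The mean among improvers is

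(90r + 180l) / (r + l) = 90 + 90 × l/(r + l).

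It depends only on the late share l/(r + l). The proportion who never recover, 1 − r − l, does not enter.

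| Group | r | l | Recovered by day 180 | Late share | Mean, improvers only |
|---|---|---|---|---|---|
| A | 33.3% | 5% | 38.3% | 13.0% | 39/0.3833 = 101.7 days |
| B, +6% | 33.3% | 6% | 39.3% | 15.3% | 40.8/0.3933 = 103.7 days |
| B, +7.5% | 33.3% | 7.5% | 40.8% | 18.4% | 43.5/0.4083 = 106.5 days |
| B, +10% | 33.3% | 10% | 43.3% | 23.1% | 48/0.4333 = 110.8 days |
| B, ahead at both visits | 40% | 10% | 50.0% | 20.0% | 54/0.50 = 108.0 days |

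The numerators are in patient-days per patient enrolled; for example, 39 = 90 × 1/3 + 180 × 0.05. Every version of B recovers at least as many patients as A at each visit and has a longer mean. The gaps run from 2.0 to 9.1 days.

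**When the reversal stops.** The means tie when the late shares tie, that is when r = l × (1/3)/0.05. Against A, B's day-90 recovery must reach 66.7% at +10%, 50% at +7.5% or 40% at +6% before the mean stops pointing the wrong way. With A at 30%+5% and B at 60%+8% there is no reversal: 36/0.35 = 102.9 days against 68.4/0.68 = 100.6 days.

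**Medians.** In every row of the table more than half of improvers are at day 90, so the medians tie there. A median reverses only if more than half of a group's improvers are late. For example, 20%+25% against 20%+10% gives medians of 180 and 90 days with 45% and 30% recovered.

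**If a rank test were used.** The plan names none. I assumed a two-sided tie-corrected Mann-Whitney test at 0.05 among improvers, with 200,000 simulated studies per cell. The 255 per group is 300 × 0.85. The table shows how often B is called significantly slower than A.

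| Patients per group | 100 | 150 | 255 | 300 |
|---|---|---|---|---|
| +10% | 20.3% | 29.2% | 46.5% | 52.9% |
| +7.5% | 8.8% | 11.7% | 17.4% | 19.8% |
| +6% | 4.3% | 5.1% | 6.4% | 6.9% |
| Identical groups | 2.3% | 2.4% | 2.5% | 2.5% |

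**With all patients kept.** Cumulative recovery by day 180 is 1/3 + 2/3 × h, where h is first recovery among those still at risk. For B at +10%, h = 0.10/0.667 = 15%, giving 43.3%. For A, h = 0.05/0.667 = 7.5%, giving 38.3%. The ordering is right.

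**Why missing EF matters to the repair.** Suppose 15% of patients at risk have no day-180 EF, at random. Censoring them leaves h, and so 43.3% and 38.3%, unchanged. Counting them as not recovered gives 33.3 + 0.85 × 10 = 41.8% and 33.3 + 0.85 × 5 = 37.6%. If only B loses 15%, the gap shrinks from 5.0 to 3.5 points (41.8% against 38.3%).

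**The case against.** The best defence is that the figure is true for what it describes. Among patients who recover, when it happens is a fair question, and B's longer mean correctly says that more of B's recoveries are late. It misleads only a reader who takes it as recovering more slowly or less. The same paragraph also plans an evaluation of baseline characteristics and recovery potential that is not limited to improvers, and it looks for individual EF patterns. The whole section is descriptive and states no decision rule.

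Much of this stands, and it limits the weight of the point. It does not remove it, because the plan says the times are compared between groups. The companion sentence could show the true ordering, but it leaves the time comparison in place with no rule for which result answers the question.

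Size is a second fair objection. The largest gap in the table, 9.1 days, is less than the ±14-day window of one visit, and a median would show no difference.

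Three stronger readings are tempting but unsupported:

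- A reader might infer that the study has up to a 53% chance of a wrong significant finding. That needs a test the plan does not name, the full 600 patients split evenly with complete EF, and the widest assumed gap.
- A reader might infer that the plan has no all-patient look at recovery. The day 90 and 180 percentages and the baseline-characteristics sentence are such looks, though incompletely specified.
- A reader might infer that the primary hypothesis is compromised. The 5% hypothesis and the sample size in section 8.1.1 do not use this comparison.

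**Conclusion.** The point holds as a limited one about the choice of analysis. As written, the between-group time comparison conditions on recovery and can reverse the ordering of groups by mean or rank. This includes a case where one group is ahead at both day 90 and day 180. Under the assumed differences the reversal is 2.0 to 9.1 days in the mean.

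The reversal depends on the better group having the larger late share among its improvers, and on a mean or rank summary being used. The documents give no recovery rates by baseline group, so its size in the actual study is unknown. The comparison is supplementary, but the change is worth making because a better method exists on data already requested.

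**What to change.** In section 8.3.1, make the between-group comparison the discrete-time cumulative incidence of first EF>35% at the day 90, 180 and 360 visits, by baseline group, among patients enrolled in the study. Specify that:

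- patients with EF≤35% stay at risk;
- death before recovery is a competing event;
- patients are censored at their last available EF, and a missing EF is not counted as non-recovery, which fits the rule in section 8.6.3.2 against replacing missing data;
- the number with an EF at each visit is reported by group, with a sensitivity result counting missing EF as not recovered.

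State that the estimate applies to patients who entered the study under section 4.1.3, including those who "were enrolled in the registry after 01-March-2019 and received an ICD prior to 90 days of WCD use". Keep improvers-only time as a labelled description, not as a comparison of speed of recovery.

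The cost is a short rewrite, slightly more analysis work, and an explicit assumption that loss of EF is non-informative. No new data, visits or patients are needed.
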